2. Secondary (comparison of each listed parameter between the prospective treatment groups in addition to comparison of each treatment group with historic controls):
 - a. Growth (rate of change)

- i. Weight, length, and head circumference at enrollment, on a weekly basis while receiving study lipid, and 2-3 weeks post-study lipid completion.
- ii. Weight, length, and head circumference at 36 weeks corrected gestational age and time of discharge.
- b. Essential fatty acid profile differences and development of deficiency
- c. Average total caloric intake for all patients on weekly basis
 - i. Average lipid dose delivered on weekly basis
- d. Feeding tolerance/ percentage of total calories from enteral feeds
 - i. Time to achievement of enteral autonomy (full enteral feedings)
 - ii. Percentage of enteral calories at end of study
 - iii. Percentage of patients in each group with enteral autonomy
- e. Transaminase, alkaline phosphatase, GGT levels at enrollment, every 4 week time point, and end of study
- f. Triglyceride concentration at baseline, weekly, and end of study
- g. Rates of other diagnoses in each study group
 - i. Retinopathy of prematurity as diagnosed by Ophthalmologic examination
 - ii. Chronic lung disease as defined by need for oxygen at time of discharge or 36 weeks corrected gestational age (if at least 28 days of age), whichever comes first.
- h. Rates of adverse and serious adverse events in each group
- i. Length of stay
- j. Two year neurodevelopmental differences using ASQ-3 screening

Study Population

Inclusion criteria

Infants admitted to the Riley Hospital Neonatal Intensive Care Unit (NICU), regardless of postmenstrual or corrected gestational age, with anticipated need for parenteral nutrition for four or more weeks PLUS one or more of the additional inclusion criteria listed below will be eligible for inclusion within the study and for randomization. Inclusion criteria include:

- Anatomic intestinal defect: Neonate with intestinal atresia, omphalocele, gastroschisis or volvulus with or without intestinal resection and need for parenteral nutrition pre or post-operatively.
- Ischemic/perforation intestinal injury: Neonates with spontaneous intestinal perforation or necrotizing enterocolitis requiring surgical intervention with need for parenteral nutrition post-operatively.

Exclusion criteria at time of study enrollment

- Infant with current weight less than 750 grams

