 1. Intralipid will be started on day 1 of parenteral nutrition at 1g/kg/d

2. Intralipid dose will be maintained at 1g/kg/d while enrolled in the study and receiving parenteral nutrition, unless other clinical concerns arise as documented by primary team.
 - a. If further caloric intake is required, Intralipid may be increased at the discretion of the treating faculty based on the needs of the individual patient.
- ii. Other parenteral nutrition components:
 1. Amino acid will be provided to meet estimated protein requirements only and will not be increased as a form of caloric intake.
 - a. Term infant approximate goal of 3 g/kg/day and preterm infant approximate goal of 3.5 – 4 g/kg/day.
 2. Glucose infusion will be utilized and advanced per standard protocol to provide remainder of estimated non-protein caloric need of each individual patient.
 - a. Maximum glucose infusion rate (GIR) while enrolled in study of 16 mg/kg/min. If further caloric intake is required, Intralipid will be increased at the discretion of the treating faculty based on needs of the individual patient.
3. All Study Patients:
 - a. Enteral feedings:
 - i. Enteral breast milk or formula choice will be at the discretion of the primary faculty physician and advanced per physician practice.
 - b. Anthropometric Measurements:
 - i. Each group will have growth monitored per standard protocol with daily weights and weekly head circumference (OFC) and length.
 - ii. Weekly measurements used for research purposes will include weekly weight, length, and OFC as documented directly by the research team (primary investigators or same registered dietician).
 - iii. Corrected measurements will also be documented with weight, length, and OFC documented at 36 weeks (+/- 3 days) corrected gestational age.
 - iv. Follow-up measurements at 2 – 3 weeks after stopping study lipid or time of discharge, whichever comes first.
 - v. At each time point, anthropometric measurements will be replicated in triplicate and the average value for that measurement will be reported within the study.
 - vi. In the event of safety concerns to the patient or research team, as raised by the research team, patient care team, or regulatory entities, the study measurements will be conducted by the bedside patient nurse. These measurements will include length board use.

- c. Diagnoses associated with Prematurity:

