 - i. Each patient's chart will be reviewed for documentation of retinopathy of prematurity or bronchopulmonary dysplasia (chronic lung disease). The absence or presence of these diseases at the time of discharge will be noted for each study patient, particularly those patients born prematurely at less than 37 weeks gestation.
- d. Length of Stay:
 - i. An ICU length of stay will be calculated for each patient based on their admit date and discharge date from the Riley NICU.
 - ii. For patients transferred to another unit prior to discharge the transfer date will also be documented. For these patients a NICU length of stay and total hospital length of stay will be calculated.
- e. Laboratory monitoring (see Table 2 below for reference schedule):
 - i. Effort will be made to draw all study lab tests along with other standard of care, routinely scheduled labs.
 - ii. The schedule outlined here is a schedule of minimum laboratory work to be obtained. These studies may be obtained more often by the patient's primary clinical team. Any lab test obtained by the primary team within 3 days for weekly labs or within one week for less frequent labs will be used in place of the research lab test.
 - iii. Of note all lab tests listed could be considered standard of care, with the exception of INR.
 - iv. Essential fatty acid profiles will be obtained every 4 weeks (28 days) while receiving study lipid regimen.
 - 1. Blood volume needed 0.3-1mL
 - 2. Considered standard of care in any patient on alternative lipid dosing, such as patients enrolled in this study.
 - 3. If diagnosed with essential fatty acid disorder, defined as triene:tetraene ratio >0.05:
 - a. If Smoflipid dose is less than 3 g/kg/d, SMOF will be increased by 0.5 g/kg/d or to 3 g/kg/d maximum
 - b. Those receiving Smoflipid at 3 g/kg/d will be changed to Intralipid at current Smoflipid dose
 - c. Those receiving Intralipid will have their dose increased by 0.5 g/kg/d to maximum of 3 g/kg/d
 - v. Total and fractionated bilirubin levels will be monitored at least once weekly (7 days)
 - vi. Liver function panel and gamma-glutamyl transferase (GGT) will be monitored at least every 2 weeks (14 days).
 - vii. Triglyceride levels will be monitored within the first 48 hours of lipid initiation and then once weekly (7 days).

1. If triglyceride level >250 mg/dL will decrease dose of study lipid by 1g/kg/d to minimum of 2 g/kg/d of Smoflipid or 1 g/kg/d three days per week for Intralipid

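### With no corrected-age limit on enrolment, retinopathy and, in some early-born infants, chronic lung disease can be settled before randomisation yet be counted as outcomes

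*Combined protocol and SAP*

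**What the plan says.** The inclusion criteria (Study Population) admit infants "regardless of postmenstrual or corrected gestational age, with anticipated need for parenteral nutrition for four or more weeks". The exclusion criteria name neither existing chronic lung disease, nor existing retinopathy, nor an age past 36 weeks.

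Three secondary outcomes are not tied to randomisation:

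- **Chronic lung disease** (Study Objectives 2.g.ii): "Chronic lung disease as defined by need for oxygen at time of discharge or 36 weeks corrected gestational age". The definition adds that the 36-week reading applies only once the infant has reached 28 days, and that the earlier of the two time points counts.
- **Retinopathy of prematurity** (Study Objectives 2.g.i) is any diagnosis on eye examination. Study Procedures 3.c.i says of retinopathy and lung disease: "The absence or presence of these diseases at the time of discharge will be noted for each study patient". No onset date, stage or baseline examination is requested.
- **Growth at a fixed age** (Study Objectives 2.a.ii): "Weight, length, and head circumference at 36 weeks corrected gestational age and time of discharge". Study Procedures 3.b.iii sets the window: "Corrected measurements will also be documented with weight, length, and OFC documented at 36 weeks (+/- 3 days) corrected gestational age". Nothing requires the window to fall after enrolment.

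A separate growth objective (2.a.i) is anchored to enrolment: "Weight, length, and head circumference at enrollment, on a weekly basis while receiving study lipid, and 2-3 weeks post-study lipid completion".

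Statistical Considerations lists retinopathy and chronic lung disease among the tabulated categorical outcomes, compared between groups by Fisher's exact test at the 5% level. Continuous variables measured through the study go to mixed models.

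**The concern.** An outcome should be open at randomisation. If an infant's status is already settled, study lipid cannot change it, and counting it as an event adds noise to the comparison.

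Late entry is plausible under this plan. Weight under 750 g and culture-confirmed sepsis within 14 days both bar enrolment until they resolve, and both can delay small preterm infants.

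The outcomes concerned bear on the protocol's own worries. The background describes lipid intake as essential to retinal development and raises lipid restriction as a possible threat to growth. A difference in retinopathy or lung disease between a reduced-dose and a standard-dose strategy would be of interest even in a pilot, and already-settled cases would blur it.

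Randomisation is stratified by diagnosis only, so with 12 to 25 infants per arm the settled cases can fall unevenly by chance. Historic controls are matched, when able, on days of parenteral lipid, diagnosis, birth gestational age and birth weight, but not on corrected age when lipid starts. The share of settled cases could therefore differ between them and the prospective groups.

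**Working it through.** The plan gives no expected rate, effect size or power for these outcomes, so there is no figure to reproduce.

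**1. Time on study lipid before the 36-week reading**

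Inputs: reading at 36 weeks corrected age; maximum 84 days on study lipid.

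Days = max(0, min(84, 7 × (36 − corrected age in weeks at enrolment)))

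| Corrected age at enrolment | Days before the reading |
|---|---|
| 30 weeks | 42 |
| 34 weeks | 14 |
| 35 weeks | 7 |
| 36 weeks or later | 0 |

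The ±3-day growth window shifts these by at most 3 days.

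**2. Whose lung-disease status is fixed**

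The 36-week reading needs an age of at least 28 days (4 weeks). Being 4 weeks old at 36 weeks means birth at 36 − 4 = 32 weeks or earlier.

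- Born at about 32 weeks or earlier, randomised after 36 weeks: fixed before randomisation.
- Born after about 32 weeks: under 28 days old at 36 weeks, so the discharge reading appears to apply. Status is still open at randomisation.
- Randomised before 36 weeks: still open, though exposure may be only days.

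**3. Retinopathy**

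An infant with retinopathy diagnosed before enrolment and still charted at discharge is recorded as present. The record cannot separate this case from one arising on study lipid.

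**4. Growth at 36 weeks**

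For an infant enrolled after the window, any 36-week value predates treatment. For an infant born after 36 weeks, such as a term infant with atresia or gastroschisis, it does not exist.

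**5. Size of the dilution**

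Let f be the share of infants whose status is fixed, with equal rates in both arms among them, and d the true difference among the rest.

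Observed difference = f × 0 + (1 − f) × d = (1 − f) × d

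For lung disease, f = (share randomised after 36 weeks) × (share of those born at about 32 weeks or earlier). If 40% were randomised late and half of those were born early enough, f = 0.40 × 0.50 = 0.20.

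Illustration, with every rate assumed: 50% v 20% among open infants (d = 30 points) and 50% in both arms among fixed infants. Power is for an exact Fisher test at 5%, taken as two-sided because the plan does not state sidedness.

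| f | Observed difference | Power, 25 per arm | Power, 12 per arm |
|---|---|---|---|
| 0 | 30 points | 51% | 21% |
| 0.20 | 24 points | 33% | 13% |
| 0.40 | 18 points | 19% | 8% |
| 0.50 | 15 points | 14% | 6% |

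Excluding the fixed infants restores the 30-point difference on fewer infants. At f = 0.20, 25 × 0.80 = 20 per arm remain and power is 41%, against 33% if they are kept. At f = 0.40, 15 per arm remain and power is 25%, against 19%.

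**The case against.** The 28-day condition matters. A reader might infer that every preterm infant enrolled after 36 weeks already has a settled lung-disease outcome. The definition does not support that: one born at 34 weeks is under 28 days old at 36 weeks and appears to be read at discharge. Using the whole late-enrolled share as f would overstate the dilution (18 points observed instead of 24 in the 40% example above). This objection stands and limits the point.

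A reader might also infer that the growth analysis as a whole is compromised. It is not. Growth is continuous and does not go to Fisher's test, the objective is headed as a rate of change, and weekly values run from enrolment. The research team takes the prospective measurements in triplicate, so a late-enrolled infant may simply lack a 36-week value. Even so, the plan does not say what happens to these infants. For controls it takes the charted value nearest the date, which may precede surgery or study-type lipid exposure.

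Nor do the documents show that safety signals would be lost. Adverse events are monitored daily from the start of study lipid, worsening of existing conditions counts, and Table 3 grades new pulmonary deterioration during infusion. The dilution affects the comparison of diagnosis rates only.

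Finally, these are unpowered secondary outcomes of a feasibility pilot of 24 to 50 infants, and randomisation balances pre-existing status in expectation. That lowers the severity. It does not make a pre-enrolment diagnosis a treatment outcome.

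**Conclusion.** The point holds in limited form. As written, the plan can count retinopathy diagnosed before enrolment as an outcome, and likewise chronic lung disease status fixed before randomisation in infants born at about 32 weeks or earlier and randomised after 36 weeks. The 36-week growth value cannot measure a treatment effect in infants enrolled or born after that age.

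Between the randomised arms the consequence is dilution by (1 − f) and chance imbalance. A reader might infer systematic bias there, but the documents do not support it. Against historic controls bias is possible, because corrected age at lipid start is not matched; neither its direction nor its size can be derived.

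The number affected is unknown because no age distribution is given. The differences and power figures above rest on assumed rates and shares and show scale only. Reading lung disease at discharge for infants under 28 days old at 36 weeks is the natural reading of the definition, though it is not spelled out. Severity is minor to moderate.

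**What to change.** 1. Record chronic lung disease and retinopathy status at randomisation as baseline characteristics. For historic controls, state an index date and do the same.
2. Count retinopathy as an outcome only if it is new, or worse than at the last examination before that date.
3. Exclude from the lung-disease comparison infants whose status under objective 2.g.ii was fixed before that date. Keep those validly read at discharge; a blanket restriction to infants randomised before 36 weeks would wrongly drop them.
4. State whether the definition in Study Objectives or the at-discharge chart review in Study Procedures 3.c.i governs lung disease, since they give different assessment times.
5. Limit the 36-week growth comparison to infants randomised before 36 weeks, and rely on change from enrolment for the rest.

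These restrictions use information known at randomisation, so the randomised comparison is preserved. The cost is protocol wording, an onset date or baseline status taken from charts already being reviewed, and smaller denominators for these secondary outcomes, which should be reported by group.

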Lipid intake in the neonatal period is crucial for retinal and brain development along and an important source of calories for growth [16]. Due to this essential nature of lipid intake during the neonatal period, concern has been raised regarding lipid restriction and its effects on neonatal growth and neurodevelopmental outcomes. Studies investigating neurodevelopmental outcomes of infants treated with lipid restriction have shown development within normal ranges for the patient's age and similar to those of patients treated with standard soy-based lipid dosing [17, 18]. Studies have shown mixed results with regards to growth and neonates treated with lipid restriction. Rollins et al showed a greater increase in weight z-score for patients on standard soy-based dosing compared to reduced dosing, but found no difference in length or head circumference [13]. Other studies have found similar growth when comparing patients both in the neonatal period and into early childhood [18, 19]. The role of the various lipid strategies in the prevention of IFALD is still unclear at this time. Further studies are needed to better understand this disease, its prevention, and its outcomes. During this study we hope to compare two possible preventative strategies and determine a future direction for studying Smoflipid and soy-based lipid reduction.

Specific Aim

This study is designed to be a single center, pilot study to evaluate the prevention of cholestasis in neonates requiring abdominal surgery with intestinal failure, divided into two treatment groups, one receiving composite lipid emulsion (Smoflipid® 20%) at standard dosing and the other receiving soy-based lipid (Intralipid® 20%) at reduced dosing. The rate of cholestasis development in the two treatment groups will be compared to a historical control cohort which received soy-based lipid (Intralipid® 20%) at standard dosing of 2 to 3 g/kg/d .

Study Objectives

1. Primary: The primary objective of this study is to determine the number of infants receiving Smoflipid at typical dosing (2-3 g/kg/d) and the number of infants receiving Intralipid reduction (1 g/kg/day) that develop cholestasis compared to historical controls receiving Intralipid at standard dosing (2-3 g/kg/day). Cholestasis will be defined as direct bilirubin greater than 2 mg/dL for at least two measurements, 5-7 days apart.

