- AST or ALT greater than 5 times the upper limit of normal within 2 weeks of enrollment

- Direct bilirubin greater than 2 mg/dL on any consecutive measurement 5-7 days apart within 2 weeks of enrollment
- Severe coagulopathy with elevated INR greater than 2.0 or clinically significant bleeding as determined by the primary and research teams
- Culture confirmed sepsis with positive blood, urine, or CSF culture within 2 weeks (14 days) of enrollment
- Renal failure requiring dialysis
- Cyanotic heart disease requiring prostaglandin therapy
- Hypertriglyceridemia (greater than 250mg/dL) at time of enrollment

Enrollment/Randomization

A maximum total of 50 prospective patients, 25 per arm, will be enrolled in the study. Patients will be eligible for enrollment if they meet the above listed enrollment criteria. Once patients are determined to meet enrollment criteria, the parents of the patient will be approached and informed consent will be obtained. Please see separate informed consent document for full consent details.

Stratified randomization will be used to divide patients into each treatment group. Patients will be initially stratified based on the diagnosis of necrotizing enterocolitis or spontaneous intestinal perforation (ischemic/perforation group) or anatomic intestinal abnormality. Once stratified based on diagnosis, patients in each stratum will then be randomized to receive either Smoflipid or Intralipid reduction as described below. Group randomization will be based on premade concealed envelopes.

This study will not be blinded as the caloric dose of the lipid strategies will vary and potentially influence other TPN dosing. Both IV lipids will be given as a solution separate from the remaining TPN. This separate IV lipid will be given as two 12 hour infusions over a 24 hour period.

In the event of slower than anticipated patient enrollment, a minimum of 24 patients (12 per treatment group) will be enrolled in order to obtain needed feasibility data.

Historic Controls

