	Blood Volume (mL)	3.1	2.8	0.8	2.2	1.7	0.5	0.8	2.2	1.7	0.5	0.8	2.2	1.7

f. Neurologic Follow-up:

i. ASQ-3 at 2 years of age:

1. All prospective patients will have an ASQ-3 obtained during the 2nd year of life (age 2 year 0 day to 2 year 364 days).
2. ASQ-3 will be obtained in one of three manners:
 - a. In person: if patient has previously scheduled appointment at Riley
 - b. Via phone: if able to confirm identity of parent or guardian
 - c. Via mail (electronic or standard): if able to confirm proper mailing address of patient and parent/guardian
3. ASQ-3 will be completed by the subject's parent or guardian with the aid of one of the primary investigators.
4. If the subject receives a score within the "monitoring zone" or below threshold of "normal" in any developmental area:
 - a. Parent/guardian will be notified of this score
 - b. If known developmental delays exist will document if patient is receiving services for delay.
 - c. If no previously known developmental delay will refer patient to their primary care physician for further developmental screening and referral for proper services and follow-up.

g. Stopping study Lipid:

- i. Once a study subject reaches one of the following parameters they will stop receiving study lipid, whichever parameter occurs first:
 1. Maximum time of 12 weeks (84 days).
 2. Cholestasis with direct bilirubin of ≥ 3 mg/dL on two consecutive lab draws at least 5-7 days apart.
 3. Lipid or parenteral nutrition discontinuation for more than one week (7 days).
 4. Subject is discharged home or transferred from Riley Hospital for Children.

- ii. Once a subject reaches one of these time points, their lipid treatment, including lipid choice and dose, will be at the discretion of their primary treating physician.
- iii. Subjects will continue to be followed by the research team in order to have the following information documented:
 - 1. Anthropometric measurements at 36 weeks corrected gestational age.
 - 2. Follow-up anthropometric measurements at 2 – 3 weeks after stopping study lipid or at the time of discharge.
 - 3. Follow-up laboratory testing at 2 – 3 weeks after stopping study lipid if still admitted to Riley Hospital for Children.
 - 4. Documentation of prematurity complications.
 - 5. Discharge and/or transfer date to determine length of stay.
 - 6. ASQ-3 screen during the second year of life.

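### The bilirubin exclusion removes only infants who already meet the full cholestasis definition, so one whose latest or only value is above 2 mg/dL can be randomised and then counted as a new case

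*Combined protocol and SAP*

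**What the plan says.** - **Entry.** The section on exclusion criteria at enrolment removes infants with "Direct bilirubin greater than 2 mg/dL on any consecutive measurement 5-7 days apart within 2 weeks of enrollment". No other criterion refers to direct bilirubin, and none requires a value to exist before enrolment.
- **Outcome.** Study Objectives, item 1: "Cholestasis will be defined as direct bilirubin greater than 2 mg/dL for at least two measurements, 5-7 days apart". It does not say that either value must follow randomisation, and it sets no baseline condition.
- **Purpose.** The Specific Aim describes a "pilot study to evaluate the prevention of cholestasis in neonates requiring abdominal surgery with intestinal failure". The primary objective counts infants "that develop cholestasis compared to historical controls receiving Intralipid at standard dosing (2-3 g/kg/day").
- **Sampling.** Study Procedures, 3.e: "Total and fractionated bilirubin levels will be monitored at least once weekly (7 days"). Table 2 lists a hepatic panel at week 0, fractionated bilirubin at week 1 and a hepatic panel at week 2. The clinical team may draw more often, and its results can stand in for study samples: "Any lab test obtained by the primary team within 3 days for weekly labs or within one week for less frequent labs will be used".
- **Stopping study lipid.** Study Procedures, 3.g, lists "Cholestasis with direct bilirubin of ≥ 3 mg/dL on two consecutive lab draws at least 5-7 days apart".
- **Analysis.** Randomisation is stratified by diagnosis group only. Categorical outcomes are compared by Fisher's exact test, with no baseline adjustment (Statistical Considerations).
- **Controls.** The same exclusions apply to the 24 historic controls, but are judged at abdominal surgery (Historic Controls).

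**The concern.** A prevention study needs infants who are free of the outcome at entry, or an outcome that separates new cases from those already under way. Here the exclusion repeats the outcome definition, so it removes infants who have completed it and admits those who are halfway there. If the raised value persists, direct hyperbilirubinaemia that began before study lipid is scored as failed prevention. With 12 to 25 infants per arm, a few such infants can move the primary result visibly. Neither the stratification nor the analysis accounts for baseline bilirubin.

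**Working it through.** **1. Entry and outcome side by side.** Both use direct bilirubin above 2 mg/dL, and both need two values 5-7 days apart. The exclusion wording is loose (it has a singular measurement), but consecutive values a set number of days apart make sense only as a pair. By contrast, another exclusion in the same list needs one value only: "Hypertriglyceridemia (greater than 250mg/dL) at time of enrollment".

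**2. Who passes the exclusion.**
- An infant with one raised value and no second value yet.
- An infant too young, or too recently transferred in, to have two values 5-7 days apart.
- An infant with two raised values 3-4 days apart, if the clinical team happens to draw that often.

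**3. When the outcome is met, if the value stays above 2 mg/dL.**
- If the week-0 value counts: weeks 0 and 1, so by about day 7.
- If both values must follow baseline: weeks 1 and 2, so by about day 14, provided weekly draws continue (reading the week-2 hepatic panel as including direct bilirubin).
- Exception: two values of 3 mg/dL or more at weeks 0 and 1 stop study lipid. The next laboratory tests the protocol requires are then 2-3 weeks later or at discharge, so it guarantees no week-2 value for that infant.

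**4. Weight of one infant.** 1/25 = 4.0 points; 1/12 = 8.3 points.

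**5. Dilution when both groups are affected alike.** The documents state no cholestasis rate, effect size or power, so there is no planned figure to reproduce and every input here is an assumption. Let q be the share who enter raised and stay raised, and p the true risk in the others. With no lipid effect in the q group, observed risk = q + (1 − q)p. Take p = 40% and 20%:

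| q | Higher-risk group | Lower-risk group | Risk ratio | Difference |
|---|---|---|---|---|
| 0 | 40% | 20% | 0.50 | 20 points |
| 4% | 0.04 + 0.96 × 0.40 = 42.4% | 0.04 + 0.96 × 0.20 = 23.2% | 0.55 | 19.2 points |
| 10% | 0.10 + 0.90 × 0.40 = 46% | 0.10 + 0.90 × 0.20 = 28% | 0.61 | 18 points |
| 20% | 0.20 + 0.80 × 0.40 = 52% | 0.20 + 0.80 × 0.20 = 36% | 0.69 | 16 points |

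**6. Historic comparison when only one group is affected.** Same assumptions, q = 10%, controls at 40% and a treated arm at 20%:
- Treated arm only: 40% − 28% = 12 points.
- Controls only: 46% − 20% = 26 points.

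The true difference is 20 points, so the error can go either way.

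**The case against.** Several counter-arguments have force.

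- **Matching entry to outcome is coherent.** The rule removes infants who already have cholestasis as the protocol defines it, and does not turn an infant away on one unconfirmed value. That stands as a rationale. It does not make the remaining cases incident.
- **Lipid may act on these infants.** A reader might infer that such events cannot be affected by the lipid strategy. The documents do not support that: the background section reports lower bilirubin and less progression in neonates moved to Smoflipid. Whether one raised value persists is observed on study lipid and may differ by arm. Only onset is fixed beforehand, and the table's assumption of no effect in these infants is just that.
- **Counting rules help in part.** A reader might infer that requiring both values after baseline changes nothing. It does help: it removes pairs that use the week-0 value, and it demands two raised values on treatment. It still admits infants who were raised at entry and remain so.
- **Size is unknown.** Nothing in the documents shows how many such infants would be enrolled, or that any would be. On the difference scale the dilution is modest.
- **It is a pilot without a power calculation.** True, but cholestasis is its primary objective, and finding design flaws is one of its stated purposes.
- **Controls face the same exclusions.** They do, but at a different time point, so the share already raised need not match.

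**Conclusion.** The gap is real on the text: the plan can count direct hyperbilirubinaemia that preceded study lipid as failed prevention. Between the randomised arms the effect is mainly dilution, with chance imbalance possible because the arms are small and stratification ignores bilirubin. Against historic controls it can bias the comparison. A reader might infer that the bias favours one side; the documents do not show which. The figures rest on assumed risks, an assumed range for q and no lipid effect in the infants raised at entry. They show sensitivity and do not forecast a result. The change is worth making because it is cheap and makes the primary outcome measure what the objective names.

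**What to change.** **Preferred.** Require the most recent direct bilirubin before randomisation to be 2 mg/dL or lower, and allow re-screening if a repeat value falls to that level. Apply the same rule to historic controls at their index date where a value is available.

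**Alternative.** Keep the criterion, but define the primary outcome as incident cholestasis in infants whose week-0 direct bilirubin is 2 mg/dL or lower. Use the same baseline condition for controls, and list infants raised at entry separately. A subset defined by a value taken before study lipid keeps the randomised comparison intact.

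Under either option, state whether both qualifying values must follow baseline.

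**Cost.** One or two sentences of text. A few infants are deferred or leave the primary count. A bilirubin result must be available before randomisation, or the week-0 sample must be taken before study lipid starts. Table 2 covers tests while enrolled, so it does not by itself guarantee a result before randomisation. Some control values may be missing, because their laboratory results are recorded only where the medical record holds them; the number missing should be reported.
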